1.0 OBJECTIVES/SPECIFIC AIMS

1.1 Introduction and Context

Depression is common in patients with opioid use disorder (OUD). In patients seeking buprenorphine-naloxone treatment for OUD, about 1 in 4 have concurrent major depressive disorder (MDD) (Savant et al., 2013). Similarly, about one third to one half of patients enrolled in methadone maintenance treatment (MMT) are depressed (Peles, Schreiber, Naumovsky, & Adelson, 2007; Zhang et al., 2016). Unfortunately, depression occurs independent of MMT treatment duration suggesting that stabilization of OUD alone is not sufficient to improve mood symptoms (Peles et al., 2007).

The relationship between OUD and depression is complex and bidirectional. Depressed patients who initiate opioid therapy are more likely to transition to long-term high-dose therapy and are at higher risk of opioid abuse or non-medical use (Sullivan, 2018). Conversely, chronic opioid use can cause neurobiological changes increasing negative affective states leading to higher suicide risk and continued opioid use (Rizk, Herzog, Dugad, & Stanley, 2021). Given this interdependence, concurrent treatment of both mood and opioid use disorder symptoms is paramount to prevent destabilization of either disorder (Vekaria et al., 2021).

1.2 Current Treatment

Current literature is limited regarding the treatment of depressed patients with OUD despite desire for positive mood being the most commonly cited reason for relapse in patients with OUD (Kadam, Sinha, Nimkar, Matcheswalla, & De Sousa, 2017; Unnithan, Gossop, & Strang, 1992). A large, randomized placebo-controlled trial of imipramine in depressed patients receiving MMT showed promising results with 57% of imipramine-treated patients considered “responders” per clinical global impression compared with 7% of placebo-treated patients. Unfortunately, drop-out was common with only 84 of 137 patients completing an adequate 6 week trial (Nunes et al., 1998). Contrastingly, an RCT involving buprenorphine + desipramine vs buprenorphine + placebo vs methadone + desipramine vs methadone + placebo failed to show efficacy of desipramine over placebo in 164 opioid- and cocaine-dependent patients. Concerningly, patients receiving buprenorphine + desipramine more frequently had urine drug screens positive for opioids than those receiving buprenorphine + placebo (Kosten, Falcioni, Oliveto, & Feingold, 2004).

Selective serotonin reuptake inhibitors (SSRIs), the first line treatment in patients with moderate-to-severe MDD have a mixed-to-negative evidence base in co-occurring MDD and OUD (Carpenter, Brooks, Vosburg, & Nunes, 2004; Petrakis et al., 1998). Regarding the treatment of depression in patients on opioid agonist therapy, a 2010 Cochrane review found there is “low evidence supporting the clinical use of antidepressants to treat depression in opioid dependence”, while also noting that current literature is limited (Pani, Vacca, Trogu, Amato, & Davoli, 2010). This finding was further supported by a subsequent meta-analysis examining antidepressant use in patients engaged with MMT (Pedrelli et al., 2011). Given the prevalence of depression in patient with OUD regardless of stage of recovery and ineffectiveness of current interventions, more effective treatments for depression in OUD are critically needed.

1.3 Purpose and Objectives of the Study

The primary objective of the proposed study is to preliminarily explore the feasibility, efficacy, and tolerability of ketamine-assisted psychotherapy in treatment of MDD in patient with OUD currently in early or sustained remission by DSM-V criteria. We seek to enroll 10 individuals with current moderate-to-severe major depression despite ongoing abstinence from opioids.

1.4 Specific Aims

To achieve these objectives, the following Specific Aims are proposed:

Specific Aim 1: To preliminarily explore the efficacy of ketamine-assisted psychotherapy in reducing symptoms of depression using the Montgomery Asberg Depression Rating Scale (MADRS).

Specific Aim 2: To preliminarily explore the tolerability of ketamine-assisted psychotherapy in treatment of depression including adverse effects, cravings and relapse

2.0 BACKGROUND

2.1 Role of Depression in Maintaining Abstinence From Opioids

Negative affect has been found to be a key mediator in failure to achieve abstinence and depression is a frequently seen comorbidity in OUD in all stages of treatment and recovery. Nearly two out of three persons entering treatment for opioid detoxification screen positive for depression (Brienza et al., 2000; Stein, Santiago Rivera, Anderson, & Bailey, 2017; Volkow, 2004). In patients seeking buprenorphine-naloxone treatment for OUD, about 1 in 4 have concurrent major depressive disorder (MDD) (Savant et al., 2013). Similarly, about one third to one half of patients enrolled in methadone maintenance treatment (MMT) are depressed (Peles et al., 2007; Zhang et al., 2016). Unfortunately, depression occurs independent of MMT duration suggesting that stabilization of OUD alone is not sufficient to improve mood symptoms (Peles et al., 2007) and desire for improvement in mood is the most commonly cited reason for relapse in OUD following initial addictions treatment (Huhn et al., 2019; Kadam et al., 2017; Volkow, Jones, Einstein, & Wargo, 2019). In addition to contributing to relapse and being a risk for unintentional overdose, OUD is an independent risk factor for completed suicide. A national cohort study of veterans (n=4,863,086) found that after controlling for psychiatric and medical comorbidities, overall substance use was still associated with a 1.67 hazard ratio for suicide in men and 2.15 in women. Furthermore, in women, OUD was associated with the highest hazard ratio for suicide of any substance of abuse at 2.33 (Bohnert, Ilgen, Louzon, McCarthy, & Katz, 2017).

2.2 Glutamatergic Dysregulation Contributes to Both Depression and Addiction Pathology

Glutamatergic dysregulation in the prefrontal cortex and mesolimbic regions (including the amygdala and the nucleus accumbens) has been implicated in addiction pathology across multiple substances of abuse (Gass & Olive, 2008). Similarly, depression has been shown to have aberrant glutamate signaling (Murrough, Abdallah, & Mathew, 2017; Niciu et al., 2014). On a cellular level, astrocytes are responsible for maintaining glutamate homeostasis (Parpura & Verkhratsky, 2012) and both depression and addiction have been linked to impaired ability of astrocytes to upregulate glutamate (Rajkowska & Stockmeier, 2013; Scofield & Kalivas, 2014). Ketamine is a noncompetitive antagonist of NMDA glutamatergic receptors which has been widely used for pain control in conjunction with general anesthesia since it was FDA approved in 1970.

2.3 Clinical Trials for Depression Treatment

Results from several meta-analyses indicate that ketamine can induce ultra-rapid improvements in depression and suicidality (Han et al., 2016; Wilkinson et al., 2017). This remission is most enduring in individuals with a family history of substance use disorders (Niciu et al., 2014). It is widely accepted that all currently approved pharmacotherapy classes for depression (serotonin reuptake inhibitors, monoamine oxidase inhibitors, and tricyclic antidepressants) are associated with a delayed onset of antidepressant activity of 2-4 weeks. A meta-analysis of nine high-quality studies showed that ketamine was significantly more effective than placebo in reducing symptoms of major depressive disorder at 24 hours, 72 hours, and 7 days post-infusion (Han et al., 2016). Additionally, results from a recent meta-analysis of ten clinical trials showed accumulating evidence that ketamine can significantly reduce suicidal ideation within 24 hours with moderate to large effect sizes (Wilkinson et al., 2017). The overall duration of antidepressant response was found to last between 3-12 days (Andrade, 2017). However, in a subgroup analysis, positive family history of alcoholism was found to be associated with a significantly longer duration of antidepressant efficacy, averaging 17 days for the family history positive group and 3.6 days for the family history negative group (Niciu et al., 2014). This suggests that the genetics underlying substance use confer a stronger response to the effects of ketamine.

2.4 Clinical Trials for Substance Use Disorder Treatment

Ketamine has shown early evidence of efficacy in the treatment of substance use disorders. One study evaluating the adjunctive use of ketamine in heroin use disorder showed that a single-session of high-

dose (2 mg/kg IM) ketamine demonstrated one-month abstinence rates of 85% compared to 55% abstinence in the low dose group (0.2 mg/kg IM), and one-year abstinence rates of 24% in the high dose group as compared to 6% in the low-dose control group (E. Krupitsky et al., 2002). In a follow-up study comparing three repeated sessions of ketamine infusions with concurrent psychotherapy to single-session treatment, abstinence rates were increased to 50% in the 3 session group as compared to the single session rate of 22% (Evgeny M Krupitsky et al., 2007). Related studies found that ketamine is useful as an adjunct to psychotherapy in the treatment of alcohol use disorder (E M Krupitsky & Grinenko, 1997) with one-year complete abstinence rates of 65.8% in the ketamine-assisted psychotherapy group compared to 24% in the control psychotherapy group. Intriguingly, the anti-depressant response to ketamine occurs primarily after the drug has been cleared from the body, suggesting that its primary effects are mediated through downstream processes. More recently, ketamine has been studied in cocaine use disorder and found to improve levels of motivation to quit using and to reduce cocaine craving (Elias Dakwar, Levin, Foltin, Nunes, & Hart, 2014) and reduce rates of cocaine self-administration by 67% relative to baseline (E Dakwar, Hart, Levin, Nunes, & Foltin, 2017; E Dakwar et al., 2018). Additionally, a single dose of ketamine combined with motivational enhancement therapy has been shown to increase abstinence and increase time to relapse in subjects with alcohol use disorder (Elias Dakwar et al., 2020) while a single dose of ketamine combined with mindfulness-based relapse prevention has yielded similar results in subjects with cocaine dependence (Elias Dakwar et al., 2019). Finally, ketamine combined with motivational enhancement therapy and mindfulness-based relapse prevention has shown promising open-label evidence for the treatment of cannabis use disorder (Azhari et al., 2021).

2.5 Novelty and Importance of the Current Study

Past studies have shown promising results for ketamine in the rapid treatment of MDD (Han et al., 2016) particularly in those with a family history of substance use (Niciu et al., 2014), however no prior studies have investigated the efficacy of ketamine-assisted psychotherapy in the treatment of depressed participants with OUD currently in early or sustained remission.

3.0 INTERVENTION TO BE STUDIED

3.1 Overview of Study Medication

Ketamine was originally FDA approved in 1970 for pain control in conjunction with general anesthesia (Ketalar, 2021). The drug has since been evaluated in academic settings for the treatment of pain and a multitude of psychiatric indications. Ketamine has been increasingly studied in academic settings and used off-label in private practice settings over the past 10 years (Wilkinson et al., 2017). Ketamine undergoes extensive hepatic first pass metabolism, with an oral bioavailability of approximately 16% (Mathew et al., 2012). For induction of anesthesia, doses of 1 to 4.5 mg/kg IV or 6.5 to 13 mg/kg IM are recommended (Ketalar, 2021).

3.2 Safety and Toxicity

The acute toxicity of ketamine has been studied in multiple species. In mature mice and rats, the intraperitoneal LD50 values have been shown to be approximately 100 times the average human intravenous dose (Ketalar, 2021). Repeated, daily intravenous injections have been studied in rats, and dogs for as long as 6 weeks with excellent tolerability (Ketalar, 2021). Similarly, twice weekly treatments in monkeys over a four- to six-week period were well tolerated (Ketalar, 2021). At sub-anesthetic doses in human clinical trials for depression, the most clinically significant physical adverse event from ketamine is a transient increase in blood pressure, which was experienced by 29.8% of participants with a mean systolic blood pressure increase of 19.6 mmHg ($p < 0.001$) and a mean diastolic blood pressure increase of 13.4 mmHg ($p < 0.001$, (Wan et al., 2015)). Small, but statistically significant changes in perception (including derealization, depersonalization, distortion of time and space, and sense of illusion) were categorized as “feeling strange or unreal” and were experienced by 11.7% of participants. The average

peak score of 4.5 on the Brief Psychotic Rating Scale is consistent with very mild symptom severity (Wan et al., 2015).

3.3 Study Drug, Dose, Mode of Administration and Justification

Ketamine is concentrated at a dose of 100 mg/ml and will be administered by intramuscular administration in the amount of 0.5 mg/kg with plan to flexibly titrate by 0.25 mg/kg each session based on tolerability to a maximum weight-based dose of 1.5 mg/kg. Total dose on a given day will be limited to 60 mg regardless of subject's weight. While formal dose response studies for depression are lacking, ketamine has been most widely studied for psychiatric indications at 0.5 to 1.0 mg/kg given intravenously. Recent studies have shown that intramuscular ketamine may be as effective as intravenous ketamine for depression and may be more practical clinically (Chilukuri et al., 2014; Xu et al., 2016). Although there are only a few studies evaluating the use of ketamine in the treatment of substance use disorders, doses in these trials have ranged from 0.5 to 0.8 mg/kg given intravenously or 2 mg/kg given intramuscularly (Jones, Mateus, Malcolm, Brady, & Back, 2018). When given intramuscularly, ketamine has a peak time of 5-30 minutes following injection and a bioavailability of 86-97% (Grant, Nimmo, & Clements, 1981). Of note, ketamine elimination clearance is high with a half-life of 2-3 hours and clearance in women that is up to 20% higher than men (Mion & Villeveille, 2013).

4.0 STUDY ENDPOINTS

4.1 Primary Outcome

Montgomery Asberg Depression Rating Scale (MADRS; (Montgomery & Asberg, 1979)). The MADRS is a clinician administered, 10-item questionnaire of depression severity. The total score ranges from 0-60, with scores of 0-6 considered normal (non-depressed), 7-19 indicative of mild depression, 20-34 indicative of moderate depression, and 35-60 indicative of severe depression. Individuals scoring 20 or higher on the MADRS will be included in the study. The MADRS evaluates the following symptoms of depression: 1) clinical appearance of sadness, 2) self-reported sadness, 3) inner tension, 4) reduced sleep, 5) reduced appetite, 6) concentration difficulties, 7) lassitude, 8) inability to feel, 9) pessimistic thought process, and 10) thoughts of suicide. The MADRS has a sensitivity of 94% and a specificity of 83%, has been shown to have high internal consistency, and correlates well with other measures of depression such as the Hamilton Depression Scale.

4.3 Exploratory Outcomes

Exploratory outcomes will include changes in characteristics related to opioid addiction including craving for opioids (Visual Analog Scale) and related areas of psychiatric functioning.

- Beck Depression Inventory (BDI-II; Beck, Steer, & Brown, 1996). A widely used 21-item self-report measure of depressive symptoms.
- Visual Analog Craving Scale (VAS; McMillan & Gilmore-Thomas, 1996). At baseline, during the interventional visits, and at each follow-up visit, subjects will be asked to report on the frequency, duration, and intensity of their opioid cravings on a 10 point (100 mm) VAS. This approach has been shown to yield a reliable and valid measure of craving in previous research.
- Timeline Follow-Back (TLFB; Linda C. Sobell, 1992): The TLFB obtains retrospective self-report of substance use by using a calendar and memory prompts to stimulate recall. Quantity and frequency assessments are made using this instrument (e.g., total amount of opioids used, percent of days using) as well as abstinence (yes/no). TLFB yields consistently high test-retest correlations and correlates well with other self-reports and collateral reports. The TLFB will assess consumption of opioids for 60 days prior to study

entry, during the interventional phase and the follow-up phase. Use of nicotine and other drugs of abuse, including prescription drugs, will also be assessed using the TLFB.

- Generalized Anxiety Disorder Screener (GAD-7; Spitzer, Kroenke, Williams, & Löwe, 2006)). The GAD-7 is a 7-item self report instrument that will assess generalized anxiety symptomology.
- Five Facets of Mindfulness Questionnaire (FFMQ; Baer, Smith, Hopkins, Krietemeyer, & Toney, 2006): The FFMQ assesses five components of mindfulness including observation, non-judgement of experience, non-reactivity to inner experience, acting with awareness, and description of experience.
- PTSD Checklist (PCL-5; Blevins, Weathers, Davis, Witte, & Domino, 2015): The PCL-5 is a 20-item self-report measure. The PCL-5 is similar in form to the PTSD Checklist (PCL) based on the DSM-5 (Weathers et al., 1993), which has excellent psychometric characteristics for screening and as a secondary indicator of PTSD symptom severity (McDonald & Calhoun, 2010).
- Insomnia Severity Index (ISI; Morin, Belleville, Bélanger, & Ivers, 2011). The ISI is a 7-item, self-report measure that assesses perceived severity of insomnia. The items sum to produce a total score (range 0–28). The ISI has an internal consistency alpha coefficient of 0.74, and has shown convergent validity with other measures such as the Pittsburgh Sleep Quality Index and sleep diaries).
- Brief Pain Inventory (BPI; Cleeland & Ryan, 1994). This 9-item questionnaire uses a 10-point Likert scale to assess the severity of pain and its interference on difference aspects of quality of life and function.
- Mystical Experience Questionnaire (MEQ). This 30-item self-report questionnaire was developed and validated through factor analysis of retrospective accounts of profound experience with psilocybin-containing mushrooms. It includes four factors: transcendence of time and space, ineffability, positive mood and mystical (internal unity, external unity, noetic quality, and sacredness) (Barrett, Johnson, & Griffiths, 2015; Maclean, Leoutsakos, Johnson, & Griffiths, 2012).

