7.3 Schedule of Assessments

The instruments to be used are standardized, have good psychometric properties, and are widely used. The schedule of study assessments is provided in **Table 1**.

Table 1: Schedule of Assessments

Instrument Name	Purpose	TIME POINT		
		BL (Wk 0)	Tx 1-8 (Wk 1-8)	Follow-up (Wk 9, 10, 12, 16)
Self-Reports and Consents				
Informed Consent	Obtain informed consent	X		
Demographics Form	Sample characterization	X		
Beck Depression Inventory-II	Self-reported assessment of depression symptom severity	X	X	X
Visual Analog Scale (VAS)	Measure subjective levels of opioid craving	X	X	X
General Anxiety Disorder (GAD-7)	Self-report of anxiety symptom severity	X	X	X
Mystical Experiences Questionnaire (MEQ)	Measure of perceptual experiences		X	
Brief Pain Inventory	Measure of pain and quality of life	X	X	X
Insomnia Severity Index (ISI)	Assess insomnia and sleep quality	X	X	X
Five Facets of Mindfulness (FFMQ)	Assess aspects of mindfulness related	X	X	X
PTSD Checklist (PCL-5)	Measure of PTSD symptoms	X	X	X
Fagerstrom Test of Nicotine Dependence (FTND)	Measure of nicotine dependence	X	X	X
Timeline Follow-Back (TLFB)	Measure of substance use	X	X	X
Clinician Assessments				
History and Physical Exam	Eligibility assessment	X		
Vital Signs Measurement	Obtain readings of blood pressure, pulse, temperature, respirations and pulse oximetry	X	X*	
Montgomery-Asberg Depression Rating Scale (MADRS)	Primary Outcome: Clinician assessed measure of depression symptom severity	X	X	X
Pre-screening Questionnaire	To assess for basic eligibility criteria before completing a full baseline visit.	X		
Laboratory and Procedural Tests				
Urine Pregnancy Test (female subjects only)	Eligibility assessment	X	X	
Urine Drug Screen	Assessment of illicit drug use	X	X	
Electrocardiogram (ECG; subjects on methadone only)	Assessment of cardiac function	X		

* Vital signs (blood pressure, pulse, respiratory rate, and pulse oximetry) will be obtained prior to treatment sessions and at 60 minutes post-treatment. Temperature will be monitored immediately prior to treatment. If there is an increase in systolic or diastolic blood pressure >30 mm Hg from baseline, or an increase in pulse rate >30 bpm from baseline, subjects will be treated with standard of care antihypertensive medications (i.e. clonidine) and the measurements will be repeated every 20 minutes until BP and pulse are within 30 points of the baseline values.

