7.4 Baseline Assessment Procedures

After completing study informed consent, participants will undergo a comprehensive evaluation to assess for inclusion and exclusion criteria. This will include self-reports and clinician assessments as shown in Table 1. This will also include assessment of depression severity and participants at highest risk for suicidality based on clinician assessment, those with a self-reported suicide attempt within the past year, and those felt likely to require hospitalization during the course of the study will be excluded. The comprehensive exam will also include a history and physical exam by the study PI (pulse oximetry measurements will be a component of the respiratory evaluation) and baseline medication evaluation for potential harmful interactions. Urine pregnancy tests will be completed for every woman of childbearing potential. Urine drug screening will be collected at baseline and prior to each ketamine session to monitor

for opioid and other illicit substance use. For patients currently taking methadone, ECG will be performed to assess for cardiac function with QTc interval of 450ms or longer being exclusionary. Assessments may be conducted by telehealth with vital signs to be provided by participant's home or pharmacy measurement.

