9.0 PROVISIONS TO MONITOR THE DATA TO ENSURE THE SAFETY OF SUBJECTS

Ongoing Clinical Monitoring: The research team will closely monitor for any increase in substance use or psychiatric distress at every study intervention visit. Subjects with clinically significant worsening of depression (i.e. development of suicidal ideation) or worsening of opioid use will be immediately referred for a higher level of treatment, and the PI will review trial safety. The PI will be responsible for assessing potential participants for inclusion and exclusion criteria, and for assessing for adverse effects (AE's) throughout the trial. AE's will be collected, documented, and reported. If the AE is not serious, the information will be recorded, managed medically as appropriate, and the event will be followed until resolution. SAEs will also be recorded on the AE Form, managed medically as appropriate, and the event is followed until resolution. In addition, the PI will review all completed AE forms for determination of SAE. All SAE reports will be sent to the MUSC IRB within 24 hours of learning of event occurrence. The PI will be responsible for withdrawal of a study participant if they become pregnant or feel that participation is no longer in a subject's best interests. Mental health symptoms will be monitored using standardized measures at each visit in order to detect any worsening symptoms. Additionally, participants will be advised to observe any signs of worsening substance use or depression symptoms, and to discuss these with the research team. All participants will be informed at the initial visit that they may terminate participation at any point. If a participant experiences distress or other problems between visits, he or she will be encouraged to contact [name] or his/her outpatient mental health provider. If a participant needs or desires immediate attention, arrangements will be made for an appointment with an experienced mental health provider. The informed consent document will provide direction to contact the study staff during office hours and/or go to the Emergency Room at any time for worsening of symptoms. In addition, participants will have access to urgent care services at MUSC. If any of the research personnel believes that a participant is medically or psychiatrically compromised by participation, the PI will be notified and will contact the participant immediately to assess concerns and assure participant safety. The PI will attempt to address all participant concerns and will set up an alternate referral for counseling for those who desire it from outside the project. All participants will review, at the initiation of participation, an informed consent document which specifically reviews potential psychological distress as a potential outcome of participation. If necessary, the participant will be asked to complete a safety plan and to call the project staff, a national hotline, or 911. The Mobile Crisis unit of Charleston County, which involves a team of police and psychiatric workers, or the EMS unit may be dispatched to the participant's home to assure safety. The investigative team has a long history of ensuring participant safety using similar methods in these populations.

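### Section 4.3 takes opioid abstinence from self-report and gives the eight treatment-phase urine screens no outcome role, while relapse (Aim 2) has no definition or data source

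*Combined protocol and SAP*

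**What the plan says.** - **Aim.** Section 1.4, Specific Aim 2, covers tolerability, "including adverse effects, cravings and relapse". No section defines relapse or says which data establish it.
- **Self-report.** Section 4.3 describes the instrument: "The TLFB obtains retrospective self-report of substance use by using a calendar and memory prompts to stimulate recall". It then assigns the opioid-use variables to it: "Quantity and frequency assessments are made using this instrument (e.g., total amount of opioids used, percent of days using) as well as abstinence (yes/no". TLFB is scheduled at baseline, during treatment and at follow-up. The support given for its validity is test-retest agreement and that it "correlates well with other self-reports and collateral reports". No biological check is named.
- **Urine.** Section 7.4 states: "Urine drug screening will be collected at baseline and prior to each ketamine session to monitor" and, as the sentence goes on, "for opioid and other illicit substance use". Table 1 (section 7.3) gives the purpose as "Assessment of illicit drug use" and marks the screen at baseline and treatments 1 to 8. It has no mark at weeks 9, 10, 12 and 16. The screen does not appear in section 4.
- **Analysis.** Section 8.1 provides only for descriptive statistics on participants. It has no derivation rule for abstinence or relapse.
- **Prescribed opioids.** Section 5.2 allows methadone and buprenorphine at a stable dose. The urine panel is not described, and no confirmatory testing is mentioned.

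**The concern.** In weeks 1 to 8 the trial holds two sources on opioid use for the same participants, and only one of them feeds a named outcome. The variable in 4.3 has one input, and a contradicting positive screen has no written route into it. If use is sometimes denied, the trial could report fewer relapses during ketamine treatment than its own samples show. For a tolerability aim that is the unsafe direction. The study is open label with a single arm, so there is no comparison in which the same under-reporting could cancel.

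Leaving the matter open has its own cost. If the source is chosen after the data are seen, then with about 10 participants one such choice moves the rate by 10 percentage points.

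**Working it through.** The plan states no relapse rate, sensitivity or power figure, so there is nothing of its own to reproduce. The check has two parts: what the text fixes, and how large the effect could be under stated assumptions.

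**1. What the text fixes.** Abstinence (yes/no) is assigned to TLFB (4.3). The urine screen is a monitoring measurement (7.3, 7.4) with no entry in section 4. Nothing combines the two, and relapse is linked to neither. The schedule gives 1 + 8 = 9 screens per participant, or 8 × 10 = 80 treatment-phase screens for 10 participants, and none at the four follow-up visits.

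**2. Effect of one discordant participant.** Reading relapse as the opposite of TLFB abstinence, with n = 10 (section 5.4), each reclassified participant moves the rate by 1/10 = 10 points. The exact 95% intervals are wide in any case: 0/10 gives 0 to 30.8%, 1/10 gives 0.3 to 44.5%, 2/10 gives 2.5 to 55.6%.

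**3. Average understatement under TLFB alone.** Let p be the true relapse proportion and u the share of relapsers who deny use but screen positive. Both are assumed: p from 10 to 40%, u from 0 to 50%. Understatement = p × u. The chance of at least one discordant participant = 1 − (1 − pu)^10.

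| p | u | Understatement | Chance of at least one of 10 |
|---|---|---|---|
| any | 0 | 0 | 0 |
| 0.10 | 0.10 | 1 point | 1 − 0.99^10 = 9.6% |
| 0.20 | 0.25 | 5 points | 1 − 0.95^10 = 40.1% |
| 0.40 | 0.50 | 20 points | 1 − 0.80^10 = 89.3% |

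**4. Gain in detection from using both sources.** With assumed sensitivities and independent errors, either-source sensitivity = 1 − (1 − s_TLFB)(1 − s_urine):
- TLFB 0.70, urine 0.50 to 0.70: 1 − 0.3 × 0.5 = 0.85, to 1 − 0.3 × 0.3 = 0.91.
- TLFB 0.50, urine 0.50 to 0.70: 1 − 0.5 × 0.5 = 0.75, to 1 − 0.5 × 0.3 = 0.85.

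If both sources miss the same light or infrequent use, the gain is smaller.

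**5. The opposite error.** Under an either-source rule, a participant who does not use has eight chances of a false positive. With independent errors and an assumed per-screen specificity of 99% or 98%, the chance of at least one is 1 − 0.99^8 = 7.7% or 1 − 0.98^8 = 14.9%. If all 10 were non-users, that is 10 × 0.077 = 0.8 or 10 × 0.149 = 1.5 participants expected to be misclassified. This is of the same order as the error in step 3, so neither rule should be reported on its own.

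**The case against.** The strongest reply is that silence is not a rule. A reader might infer that the plan scores a denying, screen-positive participant as abstinent. No section says so, or says that TLFB is used alone or that urine results are set aside. Relapse in Aim 2 is never equated with TLFB abstinence, so urine results could still count towards it. This stands, and it is why the conclusion is conditional.

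A reader might also infer that self-report error must run one way, because disclosing use has consequences. Section 9.0 says that participants with "worsening of opioid use will be immediately referred for a higher level of treatment". It does not limit this to reported use, so a positive screen could lead to the same referral, and testing before every session may reduce the incentive to deny use. Under-reporting is plausible, but the documents do not establish it.

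Nor are positive screens without effect in the trial: they serve monitoring, and section 9.0 provides for watching substance use at each intervention visit. That concerns care of the participant, however, and does not define the outcome.

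Three further points stand. A positive screen is not in itself relapse, because prescribed methadone or buprenorphine is allowed. An either-source rule carries a false-positive cost. The outcome is exploratory in a study of about 10, and both sources can be listed by participant afterwards. The last point limits the severity but does not remove the need to fix the definition beforehand, since relapse belongs to a named aim.

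**Conclusion.** The point holds in conditional form. Section 4.3 takes abstinence from self-report and gives the urine screens no outcome role, and relapse is undefined. If abstinence is derived as 4.3 describes, denied use with a positive screen in weeks 1 to 8 would be missed.

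The size is 0 if nobody denies use, and 10 percentage points per such participant with n = 10. It averages 1 to 20 points when true relapse is assumed at 10 to 40% and 10 to 50% of relapsers deny use but screen positive. No figure in the documents narrows that range. The stronger statement, that relapse is understated in this trial, is not supported.

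The change is worth making because the samples are already scheduled and relapse is part of Aim 2.

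**What to change.** In section 4.3:
- List the urine drug screen as an outcome source.
- Define relapse in weeks 1 to 8 as TLFB-reported non-prescribed opioid use, or a urine screen positive for an opioid the participant is not prescribed. Prescribed methadone or buprenorphine does not count.
- State how missing screens are handled.

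In the reporting plan (section 8.1):
- Show TLFB-only and either-source results side by side.
- List discordant cases by participant, and flag positives that were not confirmed.
- Present the follow-up period separately, since only TLFB is scheduled there.

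**Cost.** A few sentences and one table, with no new samples or visits if the existing panel suffices. The sponsor should first confirm that the panel can separate prescribed from non-prescribed opioids. If it cannot, the rule needs adapting and the cost is higher. The reported relapse rate may rise slightly, and false positives can overstate it: about 8% to 15% per non-user over eight screens at the assumed 99% to 98% specificity. Reporting both results makes that visible.
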